6. COLLECTION OF STUDY VARIABLES

The investigator will ensure that data are recorded in a timely fashion on the eCRF as specified in the study protocol and in accordance with the instructions provided. A copy of the eCRF data will be archived at the study centre.

6.1 Recording of data

The Rave Web Based Data Capture (WBDC) system will be used for data collection and query handling. The investigator will ensure that data are recorded on the eCRF as specified in the study protocol and in accordance with the instructions provided.

The investigator ensures the accuracy, completeness, and timeliness of the data recorded and of the provision of answers to data queries according to the Clinical Study Agreement (CSA). The investigator will sign the completed eCRF. A copy of the completed eCRF will be archived at the study site.

6.2 Data collection at enrolment and follow-up

6.2.1 Enrolment procedures

Each patient will undergo enrolment procedures at Visit 1. The following data will be collected:

- Demographics (including sex, date of birth, confirmation of Taiwanese ethnicity)
- Relevant medical and surgical history
- Current concomitant medications
- Targeted physical examination including vital Signs (heart rate, blood pressure)
- Safety laboratory blood analyses (clinical chemistry and haematology)
- Urine pregnancy test (for females of child bearing potential)
- 12-lead ECG
- Myocardial necrosis biomarker

6.2.2 Follow-up procedures

Patients will have routine visits as outlined in Table 2. Any new suspected endpoint events, SAEs and current medications will be recorded. In order to determine whether or not clinical events meet the endpoint definition, it will be the responsibility of the Investigator to obtain all necessary source documents, including medical records from institutions where a hospitalisation may have occurred.

6.3 Efficacy

Suspected clinical efficacy endpoints will be collected in the eCRF. These events will be identified using standard questioning of the patient at each visit, or by information that the investigator may receive as part of standard medical practice. Safety endpoint events will be identified similarly.

For each suspected endpoint, the investigator will collect relevant additional source information where required, determine whether a safety or efficacy endpoint has occurred, and record their finding on the eCRF.

6.3.1 CV death

All deaths reported post-enrolment will be recorded and classified by the investigator as CV or non-CV.

6.3.2 MI

MI is diagnosed on the basis of elevation of myocardial necrosis biomarkers typical of acute MI with **at least 1 of the following:**

1. Recurrent cardiac ischaemic symptoms ≥ 20 minutes at rest
2. Development of new pathological Q waves on the ECG
3. New or presumed new ECG changes indicative of ischaemia in 2 or more contiguous leads (ST-segment elevation, ST-segment depression or T-wave inversion)

6.3.3 Stroke

A stroke is defined as a neurological deficit caused by an ischaemic or haemorrhagic central nervous system event with residual symptoms at least 24 hours after onset or leading to death.

Stroke will be further sub-classified as:

4. Ischaemic:

Ischemic stroke is defined as an infarction of the central nervous system tissue that results from a thrombus or embolus impairing central nervous system perfusion (and not primarily due to haemorrhage) with residual signs or symptoms lasting at least 24 hours after onset or leading to death. Haemorrhage may be a consequence of ischemic stroke. In this situation, the stroke should be recorded as an ischemic stroke with hemorrhagic transformation rather than a hemorrhagic stroke event.

5. Haemorrhagic:

Hemorrhagic stroke is defined as an acute episode of focal or global cerebral or spinal dysfunction with a documented cause of intracranial haemorrhage on imaging (eg, computed tomography (CT) scan or magnetic resonance imaging (MRI) scan) either in the cerebral parenchyma, or in the subdural, epidural or subarachnoid space with residual signs or symptoms at least 24 hours after onset or leading to death. Evidence of hemorrhagic stroke obtained from lumbar puncture, neurosurgery, or autopsy can also confirm the diagnosis.

6. Unknown/No imaging performed: if the type of stroke could not be determined by imaging or other means (from lumbar puncture, neurosurgery, or autopsy) but is judged to fulfill the stroke definition above, the stroke will be classified as ischaemic for purposes of the study.

6.4 Safety

The Principal Investigator (PI) is responsible for ensuring that all staff involved in the study is familiar with the content of this section.

6.4.1 Definition of adverse events

An adverse event (AE) is the development of an undesirable medical condition or the deterioration of a pre-existing medical condition following or during exposure to a pharmaceutical product, whether or not considered causally related to the product.

An undesirable medical condition can be symptoms, eg, nausea, chest pain, or signs, eg, tachycardia, enlarged liver, or the abnormal results of an investigation, eg, laboratory findings, electrocardiogram. In clinical studies an AE can include an undesirable medical condition occurring at any time after the patient has signed informed consent, including run-in or washout periods, even if no specific treatment has been administered.

The term AE is used to include both serious and non-serious AEs

6.4.2 Definitions of serious adverse event

A serious adverse event (SAE) is an AE, occurring at any study phase (ie, run-in, treatment, washout, follow-up), that fulfils one or more of the following criteria:

Results in death

Is immediately life-threatening

Requires in-patient hospitalisation or prolongation of existing hospitalisation

Results in persistent or significant disability/incapacity or substantial disruption of the ability to conduct normal life functions

Is a congenital abnormality/birth defect

Is an important medical event that may jeopardize the subject or may require medical intervention to prevent one of the outcomes listed above.

For further guidance on the definition of a SAE, see Appendix B to the Clinical Study Protocol.

6.4.3 Recording of adverse events

Time period for collection of adverse events

AE/SAEs will be recorded from the time of signature of informed consent throughout the treatment period, including the follow-up period, to last contact.

Follow-up of unresolved adverse events

Any AEs that are unresolved at the subject's last AE assessment in the study are followed up by the investigator for as long as medically indicated, but without further recording in the eCRF. AstraZeneca retains the right to request additional information for any subject with ongoing AE(s)/SAE(s) at the end of the study, if judged necessary.

Variables

The following variables will be collect for each AE;

- AE (verbatim)
- The date when the AE started and stopped
- Whether the AE is serious or not
- Investigator causality rating against the Investigational Product (yes or no)
- Action taken with regard to investigational product
- Outcome.

In addition, the following variables will be collected for SAEs:

- Date AE met criteria for serious AE
- Date Investigator became aware of serious AE
- AE is serious due to
- Date of hospitalisation
- Date of discharge
- Probable cause of death
- Date of death
- Autopsy performed
- Causality assessment in relation to Study procedure(s)

- Causality assessment in relation to other medication

Description of AE

The following definitions for intensity rating are:

- mild (awareness of sign or symptom, but easily tolerated)
- moderate (discomfort sufficient to cause interference with normal activities)
- severe (incapacitating, with inability to perform normal activities)

It is important to distinguish between serious and severe AEs. Severity is a measure of intensity whereas seriousness is defined by the criteria in Section 6.4.2. An AE of severe intensity need not necessarily be considered serious. For example, nausea that persists for several hours may be considered severe nausea, but not a SAE. On the other hand, a stroke that results in only a limited degree of disability may be considered a mild stroke but would be a SAE.

Causality collection

The Investigator will assess causal relationship between Investigational Product and each AE, and answer 'yes' or 'no' to the question 'Do you consider that there is a reasonable possibility that the event may have been caused by the investigational product?'

For SAEs causal relationship will also be assessed for other medication and study procedures. Note that for SAEs that could be associated with any study procedure the causal relationship is implied as 'yes'.

A guide to the interpretation of the causality question is found in Appendix B to the Clinical Study Protocol.

Adverse Events based on signs and symptoms

All AEs spontaneously reported by the subject or reported in response to the open question from the study personnel: '*Have you had any health problems since the previous visit/you were last asked?*', or revealed by observation will be collected and recorded in the eCRF. When collecting AEs, the recording of diagnoses is preferred (when possible) to recording a list of signs and symptoms. However, if a diagnosis is known and there are other signs or symptoms that are not generally part of the diagnosis, the diagnosis and each sign or symptom will be recorded separately.

Adverse Events based on examinations and tests

The results from protocol mandated laboratory tests and vital signs will be summarised in the clinical study report. Deterioration as compared to baseline in protocol-mandated laboratory values, vital signs should therefore only be reported as AEs if they fulfil any of the SAE criteria or are the reason for discontinuation of treatment with the investigational product.

If deterioration in a laboratory value/vital sign is associated with clinical signs and symptoms, the sign or symptom will be reported as an AE and the associated laboratory result/vital sign will be considered as additional information. Wherever possible the reporting investigator uses the clinical, rather than the laboratory term (eg, anaemia versus low haemoglobin value). In the absence of clinical signs or symptoms, clinically relevant deteriorations in non-mandated parameters should be reported as AE(s).

Deterioration of a laboratory value, which is unequivocally due to disease progression, should not be reported as an AE/SAE.

Any new or aggravated clinically relevant abnormal medical finding at a physical examination as compared with the baseline assessment will be reported as an AE.

NB. Cases where a subject shows an AST **or** ALT $\geq 3 \times \text{ULN}$ **and** total bilirubin $\geq 2 \times \text{ULN}$ may need to be reported as SAEs, please refer to Appendix D ‘Actions required in cases of combined increase of Aminotransferase and Total Bilirubin – Hy’s Law’, for further instructions.

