Investigational product, dosage and mode of administration

Ticagrelor 180mg loading dose taken orally, followed by 90mg bd

Comparator, dosage and mode of administration (Not applicable)

Duration of treatment

12 months.

Outcome variable(s):

Primary variables

- PLATO-defined fatal/life-threatening bleedings during 1 year follow up in Taiwanese NSTEMI patients treated with ticagrelor.
- PLATO-defined major bleedings during 1 year follow up in Taiwanese NSTEMI patients treated with ticagrelor.
- PLATO-defined major + minor bleedings during 1 year follow up in Taiwanese NSTEMI patients treated with ticagrelor.
- Serious adverse events other than bleeding during 1 year follow up in Taiwanese NSTEMI patients treated with ticagrelor.
- Major CV events (cardiovascular death, MI or stroke) during 1 year follow up in Taiwanese NSTEMI patients treated with Ticagrelor.

Statistical methods

The primary efficacy analysis will be based on the intent-to-treat principle using the full analysis set of investigator adjudicated events. The analysis set will include all patients who have taken at least one dose of study medication, regardless of protocol adherence or continued participation in the study. The cumulative incidence will be presented with K-M% with 95% CI.

Statistical methods will be descriptive. For continuous data, descriptive statistics will be presented as number of patients (n), mean, standard deviation (SD), median, minimum and maximum. For categorical data, the frequency and percentage of patients in each category will be presented. Counts that are zero will be displayed as “0”. Percentages will be based on non-missing data unless otherwise specified.

	PAGE
TITLE PAGE	1
REVISED PROTOCOL SYNOPSIS	2
TABLE OF CONTENTS	4
LIST OF ABBREVIATIONS AND DEFINITION OF TERMS	9
1. INTRODUCTION	11
1.1 Background	11
1.2 Research hypothesis	11
1.3 Rationale for conducting this study	12
1.4 Benefit/risk and ethical assessment.....	13
2. STUDY OBJECTIVES.....	13
2.1 Primary objective	13
2.2 Secondary objective (Not applicable)	13
3. STUDY PLAN AND PROCEDURES	13
3.1 Overall study design and flow chart	14
3.1.1 Duration of Study.....	17
3.1.2 Enrolment.....	17
3.1.3 Protocol Visits.....	17
3.1.4 Premature Treatment Discontinuation	17
3.2 Rationale for study design, doses and control groups.....	17
3.2.1 Rationale for study design.....	17
3.2.2 Patients and Choice of endpoints	17
3.2.3 Dose regimens.....	17
3.2.4 Limitations of the study	18

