6.4.4 Reporting of serious adverse events

All SAEs have to be reported, whether or not considered causally related to the investigational product, or to the study procedure(s). All SAEs will be recorded in the eCRF.

If any SAE occurs in the course of the study, then investigators or other site personnel inform appropriate AstraZeneca representatives immediately, or **no later than 24 hours** of when he or she becomes aware of it.

The designated AstraZeneca representative works with the investigator to ensure that all the necessary information is provided to the AstraZeneca Patient Safety data entry site **on the day** of initial receipt for fatal and life threatening events **and within five calendar days** of initial receipt for all other SAEs.

For fatal or life-threatening adverse events where important or relevant information is missing, active follow-up is undertaken immediately. Investigators or other site personnel inform AstraZeneca representatives of any follow-up information on a previously reported SAE immediately, or **no later than 24 hours** of when he or she becomes aware of it.

Once the Investigators or other site personnel indicate an AE is serious in the WBDC system, an automated email alert is sent to the designated AstraZeneca representative.

If the WBDC system is not available, then the Investigator or other study site personnel reports a SAE to the appropriate AstraZeneca representative by telephone.

The AstraZeneca representative will advise the Investigator/study site personnel how to proceed.

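### Section 6.4.3 bars SAE reporting of laboratory changes unequivocally attributed to disease progression, with no exception for serious ones, and so conflicts with Section 6.4.4

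*Protocol*

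**What the plan says.** Section 6.4.3, under the heading on examinations and tests, contains several rules for laboratory findings.

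- For deteriorations in protocol-mandated laboratory values and vital signs, it says they "should therefore only be reported as AEs if they fulfil any of the SAE criteria or are the reason for discontinuation of treatment".
- Where clinical signs accompany the change, "the sign or symptom will be reported as an AE and the associated laboratory result/vital sign will be considered as additional information".
- A later sentence adds: "Deterioration of a laboratory value, which is unequivocally due to disease progression, should not be reported as an AE/SAE".

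The definitions and the reporting rule are in neighbouring sections. Section 6.4.1 counts as an AE "the deterioration of a pre-existing medical condition following or during exposure to a pharmaceutical product, whether or not considered causally related to the product", and its examples of an undesirable condition include "the abnormal results of an investigation, eg, laboratory findings, electrocardiogram". Section 6.4.2 makes any AE that meets one of its listed criteria an SAE. Those criteria include prolongation of an existing hospital stay. Section 6.4.4 says: "All SAEs have to be reported, whether or not considered causally related to the investigational product, or to the study procedure(s)." It also requires all of them to be entered in the eCRF and notified to the sponsor within 24 hours of awareness.

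One of the five primary variables in the synopsis is "Serious adverse events other than bleeding during 1 year follow up in Taiwanese NSTEMI patients treated with ticagrelor".

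**The concern.** A site that sees a serious laboratory deterioration and is certain it comes from the underlying disease has two instructions. Section 6.4.4 tells it to report, and the sentence in 6.4.3 tells it not to. It cannot follow both.

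Two features make this more than untidy wording. First, the withheld class feeds a primary variable in a single-arm, open-label study, where no control rate helps to separate disease from drug. Second, the filter acts on presumed cause before the event is recorded as an SAE. The protocol already has a place for cause, the yes/no causality question asked for every AE. An event recorded with causality answered no can still be counted or set aside at analysis. An event never recorded as an SAE carries no seriousness criterion, hospitalisation dates or causality rating, and it triggers no 24-hour notice.

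**Working it through.** **The protocol's own figure.** Section 12.3 gives a precision of ±4.3% for a 5% rate in 100 patients. The Wald half-width is 1.96 × √(0.05 × 0.95 / 100) = 0.0427, or 4.3 points, so the figure reproduces. It concerns fatal/life-threatening bleeding, and the present point does not depend on it.

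**The textual check.** Take a laboratory deterioration that prolongs a hospital stay and that the investigator regards as unequivocally due to the disease.

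1. Section 6.4.1: a laboratory finding can be an AE, and worsening of an existing condition counts whether or not the product caused it. The change is an AE.
2. Section 6.4.2: prolonged hospitalisation is a seriousness criterion. The AE is an SAE.
3. Section 6.4.4: all SAEs are reported and entered in the eCRF. The change must be reported.
4. Section 6.4.3, the disease-progression sentence: it names AE and SAE together and has no exception for seriousness. The change must not be reported.

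Steps 3 and 4 cannot both be obeyed, and the text gives no order of precedence. The conflict comes from the word *all* in 6.4.4 combined with the definitions. The causality clause in 6.4.4 refers only to the investigational product and study procedures, so it does not by itself settle cases blamed on the disease.

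**Which events are exposed.** An event is lost from the primary variable only if all of the following hold:

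- it meets an SAE criterion;
- it is a laboratory change with no sign, symptom or diagnosis that 6.4.3 would make reportable in its own right;
- it is judged unequivocally due to disease progression.

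The set is small but need not be empty. Patients are enrolled in hospital within 24 hours of symptom onset, and AE recording starts at consent. An isolated creatinine rise that delays discharge from the index stay could therefore fall in it.

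**What is still captured.** Section 6.4.3 has mandated laboratory results summarised in the study report, and Section 11.2.1 has a sponsor medical expert review laboratory data for other significant adverse events (OAEs). Table 2 schedules laboratory tests at Visit 1, Visit 2 (6 weeks), the premature discontinuation visit and Visit 6 (12 months), with extra tests at the investigator's discretion. A value measured at some other time, for example during an admission, is not assured of this route. An OAE label also does not return an event to the SAE count.

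**Size.** The protocol gives no expected rate of non-bleeding SAEs and no number of laboratory-only SAEs, so the under-count cannot be computed. Only the unit effect can be stated: 1/100 = 1.0 percentage point for each patient whose only non-bleeding SAE is withheld. For scale, the 95% half-widths at assumed true rates are:

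- 10%: 1.96 × √(0.10 × 0.90 / 100) = 5.9 points
- 20%: 1.96 × √(0.20 × 0.80 / 100) = 7.8 points
- 30%: 1.96 × √(0.30 × 0.70 / 100) = 9.0 points

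These three rates are assumptions without a source in the protocol.

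**The case against.** The strongest reply is that the sentence is narrow by design. It exempts a laboratory value, not a clinical event, and only where the cause is beyond doubt. A rise of uncertain origin, which is where a drug signal could hide, stays reportable. Section 6.4.3 prefers diagnoses to lists of signs and clinical terms to laboratory terms, so a rise in creatinine or liver enzymes from worsening heart failure would normally be reported as heart failure. Scheduled values remain in the database and are reviewed by someone other than the investigator. All of this stands, and it limits the size of the problem. It does not remove the conflict, because the sentence still names SAEs and gives no exception.

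The reply also disposes of several stronger readings that a reader might infer:

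- *That any laboratory change put down to the disease is barred.* The word *unequivocally* excludes this.
- *That the sentence flatly contradicts the earlier laboratory rule.* That rule says such changes are reported only if a condition is met. This is a necessary condition, and a later sentence can add an exception to it. It is a tension, not a contradiction.
- *That it contradicts the note on combined aminotransferase and bilirubin rises.* The note says only that these may need SAE reporting and refers to Appendix D. Appendices B and D are not in the text available, so no conflict can be shown.
- *That the information is always lost beyond recovery.* Scheduled values are kept, summarised and reviewed.

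**Conclusion.** The point holds as a conflict between a stated reporting exclusion and the protocol's own SAE definitions and reporting rule. It touches a primary variable and expedited reporting. The passages must be reconciled, and disease progression, which the text shown leaves undefined for NSTEMI, should not be left to each open-label investigator to interpret where a serious event is concerned.

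The effect is probably small. A reader might go further and infer a material downward bias in the non-bleeding SAE rate, for instance by supposing that a few patients are filtered out. The protocol gives no number from which such a bias could be derived. A loss of one or two patients would also lie well within the sampling error shown for the assumed rates. The case for the change is that the rules conflict and the remedy is cheap; no distortion of the result has been demonstrated. The conclusion rests on the protocol text alone, and Appendices B and D might contain guidance that narrows it further.

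**What to change.** Limit the sentence in Section 6.4.3 to non-serious changes and state which rule prevails. Suggested text:

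*A laboratory deterioration that is unequivocally due to progression of the underlying disease need not be reported as an AE, provided that it meets no SAE criterion and does not lead to discontinuation of investigational product. A laboratory deterioration that meets any SAE criterion is reported under Section 6.4.4 whatever its presumed cause. The investigator answers the causality question for it in the usual way.*

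The last sentence matters. Causality should not be pre-set to no when the disease is blamed, because Section 6.4.3 asks whether the product could reasonably have caused the event, and a disease explanation does not by itself exclude that.

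The cost is a change to one short paragraph of the protocol and the matching eCRF instructions, and possibly a few more SAE forms. No assessments are added, and the sample size is unaffected.
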